- Resting trough-cuff seated SBP ≥ 140 and ≤ 179 mmHg based on the mean of at least 2 current consecutive clinic blood pressure readings at Screening and at the end of the placebo run-in period (Visit 3) and at randomization (Visit 4), AND
- Currently on 2 or more antihypertensive medications, which have been titrated upward as
 tolerated to recommended hypertension target doses (such as diuretics [except for
 potassium-sparing diuretics], renin-angiotensin system blockers, and/or calcium channel
 blockers. One of the antihypertensive medications must be high ceiling diuretic (loop or
 thiazide-like), unless there is a documented intolerance or contraindication to diuretic therapy.
 The doses of the antihypertensive medications should be stable without any dose adjustment
 during the 30 days prior to randomization; OR
- Patients with uncontrolled hypertension and moderate-to-severe CKD with documented history of intolerance to multiple antihypertensive medications on fewer than 2 antihypertensive medications.

All patients are to have a serum potassium $\leq 4.8 \text{ mmol/L}$ at both Screening and the end of the placebo run-in period; and a mean (Visit 1 and Visit 3) eGFR ≥ 15 and $\leq 44 \text{ mL/min/1.73 m}^2$.

STUDY DESIGN AND DURATION:

This is a Phase 2, randomized, double-blind, placebo-controlled, multi-center study to assess the efficacy, safety, and pharmacokinetics (PK) of KBP-5074 in patients with moderate-to-severe CKD and uncontrolled hypertension (Grade 1 to 2 systolic hypertension – ESC/ESH).

The study will enroll approximately 240 patients, randomized in a 1:1:1 ratio to 1 of 3 treatment groups (80 patients in each group): KBP-5074 0.25 mg once daily (QD), KBP-5074 0.5 mg QD, or placebo QD. Randomization will be stratified to balance enrollment for key variables that may influence safety and/or efficacy evaluations, including eGFR (\geq 30 versus < 30 mL/min/1.73 m²) and SBP (\geq 160 versus < 160 mmHg). Approximately 30% of patients enrolled in the study should have eGFR in the range of 15 to 29 mL/min/1.73 m². The study will be approximately 5 months in duration with 84 days of double-blind treatment.

The study will consist of up to a 4-week screening period, 2-week open-label (placebo) run-in period, 84-day double-blind treatment period, and a 4-week post-treatment safety follow-up period.

Plasma samples for PK analysis will be collected from all patients. A total of 4 PK samples will be collected from each patient, including at Day 1 (prior to discharge), Day 14 pre-dose, Day 28 pre-dose, and the End of Study Visit (Day 112)/Early Termination Visit. The pre-dose samples assume that patients will be dosed in the unit on the days above. If patients are not dosed in the

unit on those days, a PK sample will be collected during each of these visits and the date and time of the last dose will be recorded.

Safety will be assessed systematically, and an independent data monitoring committee will perform cumulative reviews of safety data at regular intervals during the study.

Serum potassium levels, serum creatinine, and blood pressure will be monitored throughout the study and clinically significant changes will be reported as adverse events of special interest.

At Screening and the end of the placebo run-in period (Visit 3), patients must have uncontrolled hypertension (Grade 1 to 2 systolic hypertension – ESC/ESH), defined as resting trough-cuff seated SBP \geq 140 and \leq 179 mmHg, based on the mean of at least 2 current consecutive blood pressure readings in the clinic, a serum potassium \leq 4.8 mmol/L at Screening and the end of the placebo run-in period (Visit 3), and a mean (Visit 1 and Visit 3) eGFR \geq 15 and \leq 44 mL/min/1.73 m².

In all cases, dose and frequency of concurrent antihypertensive medications are expected to be maintained without dose adjustment for 30 days prior to randomization in order to ensure that blood pressure is stable. In general, patients should not add or adjust dose and/or types of the antihypertensive medications they are receiving during the screening period and throughout the duration of the study (unless they develop symptomatic hypotension). The dose of diuretic may be adjusted based on developing or resolved edema, weight gain or loss, or pulmonary congestion.

Patients will be advised to maintain their normal diet and avoid unhealthy levels of alcohol use or potassium-rich foods/drinks during the study period. No potassium supplements are permitted, unless clinically indicated to treat hypokalemia on an emergent basis until serum potassium values are within the normal range. The use of potassium-sparing diuretics is not permitted within 3 months prior to Screening until the end of study assessments. Intermitted or chronic use of potassium-binding drugs is not permitted for 3 months prior to Screening until the end of study assessments.

After completion of the screening period and the qualifying Screening Visit, patients who meet all eligibility criteria (except those criteria scheduled to be assessed after the Screening Visit), will enter the 2-week, open-label (placebo) run-in period. At the end of the run-in period (Visit 3), patients will be reassessed for eligibility, including persistence of uncontrolled hypertension and compliance with open-label placebo received during the run-in period and current antihypertensive medication. If a patient's compliance is < 80% or > 120%, the patient will not be eligible for the study, and no further visits will be performed.

If a patient is found to be ineligible during Screening, a single rescreening is allowed if the Investigator believes that the patient's medical condition has changed, and the patient may be eligible before the rescreening tests. Please note that a new patient number should be assigned to any rescreened patient, and all of the procedures defined in the protocol for the Screening Visit and during the run-in period must be repeated.

Patients who meet all eligibility criteria at Visit 4/Day 1 will be randomized (stratified based on eGFR \geq 30 versus < 30 mL/min/1.73 m² and SBP \geq 160 versus < 160 mmHg) into the study on Day 1. All randomized patients will receive double-blind treatment for 84 days. Patients will be followed for 4 weeks for safety assessments after the last dose of study drug. Antihypertensive

therapy may be modified if necessary during the safety assessment, following withdrawal of the study drug, to maintain blood pressure control.

A subset of up to 40 patients per treatment group who agree to participate in 24-hour ABPM and still meet eligibility criteria at the end of the run-in period (Visit 3) will undergo 24-hour ABPM on Day -1, Day 40, and Day 82.

DOSAGE FORMS AND ROUTE OF ADMINISTRATION:

At the Day 1 Visit, eligible patients will be randomized in a 1:1:1 ratio to the following treatment groups:

- KBP-5074 0.25 mg QD orally,
- KBP-5074 0.5 mg QD orally, or
- Placebo QD orally.

EFFICACY VARIABLES:

The primary efficacy variable is the change in trough-cuff resting seated SBP from baseline to Day 84.

The key secondary efficacy variables include the following:

- Change in trough-cuff seated DBP from baseline to Day 84;
- Change in 24-hour mean, daytime mean, nighttime mean, morning mean, last 6 hours of the dosing interval mean, SBP, DBP, MAP, and HR from baseline to Day 84 as measured by 24-hour ABPM in a subset of up to 40 patients per treatment group; and
- Change and percent change in UACR from baseline to Day 84 (for patients with albuminuria [defined as UACR > 300 mg/g] or microalbuminuria [defined as UACR in the range of 30 mg/g to 300 mg/g]).

PHARMACOKINETIC VARIABLES:

Plasma samples for PK analyses will be collected from all patients at the visits indicated on the Schedule of Procedures (Appendix A).

PHARMACODYNAMIC VARIABLES:

The pharmacodynamic (PD) variable of this study is change in serum aldosterone and plasma renin levels from baseline to Day 84.

Serum/plasma samples will be stored at central laboratory for determination of various additional biomarkers, including but not limited to galectin-3, N-terminal of the prohormone brain natriuretic peptide, interleukin-6, collagen biomarkers, and C-reactive protein. The panel of biomarkers and time points for analysis will be determined prior to the database lock.

SAFETY VARIABLES:

Safety variables will include adverse events, vital signs (pulse rate, respiratory rate, and oral temperature), clinical laboratory findings, 12-lead electrocardiograms (ECGs), and physical examination findings.

The following serum potassium/hyperkalemia-related parameters and renal function-related parameters will be collected and evaluated:

- Incidence of hyperkalemia (defined as serum potassium ≥ 5.6 mmol/L), incidence of severe hyperkalemia (defined as serum potassium ≥ 6.0 mmol/L), and incidence of patients with serum potassium > 5.0 mmol/L;
- Change in serum potassium levels from baseline to Day 84; and
- Change in eGFR and creatinine levels > 30% throughout the study period.

STATISTICAL ANALYSES:

The Intent-to-Treat (ITT) Population will consist of all randomized patients who take at least 1 dose of randomized study drug, have a baseline SBP measurement, and have at least 1 post-randomization SBP measurement. The ITT Population is the primary analysis population. All efficacy analyses will be performed for the ITT Population.

The Per-Protocol Population will include all ITT patients who have completed the 84-day double-blind treatment period without any major protocol deviations or violations. The Per-Protocol Population will be used to assess robustness of the primary analysis results. The major protocol deviations will be pre-specified prior to unblinding treatment codes for analyses.

The Safety Population will include all randomized patients who receive at least 1 dose of randomized study drug.

The population-pharmacokinetic (PPK) Population will include all randomized patients who receive at least 1 dose of randomized study drug and have at least 1 measurable concentration of total KBP-5074.

The primary efficacy analysis is to evaluate the change in trough-cuff seated SBP from baseline to Day 84 for the KBP-5074 doses compared to placebo. The endpoint for each patient is defined as the Day 84 cuff seated SBP measurement. If the measurement at this visit is missing or the patient discontinues early, the last post-baseline measurement during the double-blind period will be used.

The primary efficacy analysis will be carried out using a 2-way analysis of covariance (ANCOVA) model with treatment, baseline eGFR level (≥ 30 versus < 30 mL/min/1.73 m²), and background antihypertensive medication (2 or more) as factors, and the baseline SBP value as a covariate. The least-squares means, standard errors, and the 2-tailed 95% confidence intervals (CIs) for each treatment group and for the comparison will be estimated. The treatment difference between KBP-5074 doses and placebo will be estimated from the ANCOVA model. No multiple comparison adjustment will be used for this Phase 2 study.

The primary efficacy analysis will be based on the ITT Population. Other imputation methods for the primary efficacy endpoint will be explored. The supportive analysis will be carried out for the

primary efficacy variable based on the Per-Protocol Population to examine the impact due to premature dropouts and/or major protocol deviations or violations.

For continuous secondary efficacy variables, the same ANCOVA model will be used as the primary efficacy analysis. For categorical data, logistic regression or chi-square test will be used. Treatment effects will be evaluated between KBP-5074 doses and placebo.

Safety assessments will include monitoring of adverse events, vital signs (pulse rate, respiratory rate, and oral temperature), clinical laboratory findings, 12-lead ECGs, and physical examination findings. All safety analyses will be conducted on the total patient cohort based on the Safety Population.

The assessment of safety will be based primarily on the frequency of patients with adverse events and clinical laboratory abnormalities. Other safety data will be summarized as appropriate.

Adverse events will be coded using the Medical Dictionary for Regulatory Activities. Reports will be provided to the Medical Monitor for approval of the coded terms after the database is clean, prior to unblinding. The number and frequency of patients with treatment-emergent adverse events (TEAEs) (ie, those adverse events that newly occur or worsen in severity during the study) will be summarized by system organ class and preferred term. Serious adverse events (SAEs) and TEAEs related to study drug will be summarized in the same manner. A list of patients with SAEs and those who discontinue from the study due to an adverse event will be provided.

Summary statistics by treatment group at baseline, at all post-randomization visits, and changes from baseline to the post-randomization visits for laboratory values will be provided. Occurrence of significant abnormalities in laboratory values from baseline will be summarized by treatment group. Vital signs, body weight, and physical examination findings will be summarized.

The analysis of the PK/PD relationship will be explored. Population PK models will be built using a nonlinear mixed effects modeling technique with NONMEM software based on the PPK Population. Different PK models will be attempted to fit the PK concentration-time data. After the PPK modeling, a population PD approach will be used to explore the concentration-effect relationships. Different PD models will be attempted to fit the concentration-effect data. All PD exploration will be based on the ITT Population.

SAMPLE SIZE DETERMINATION:

For this Phase 2 study, the primary efficacy endpoint is the change in trough-cuff resting seated SBP from baseline to Day 84. Assuming an observed treatment difference of SBP changes between the KBP-5074 group and the placebo group is 5 mmHg, and a standard deviation of change from baseline of 15 mmHg, with 80 patients/group, the CI of the observed difference would not include 0. Assuming 10% to 15% dropout post randomization, 80 patients/group or a total of 240 patients would be needed for this Phase 2 study. Additional sample size estimates based on sample size needed per group to ensure that the observed 95% CI does not include 0 are shown below. No multiple comparison adjustment will be applied.

Sample Size Estimates

		Observed Treatment Effect		
Standard Deviation	4 mmHg	5 mmHg	6 mmHg	
14 mmHg	109	70	48	
15 mmHg	125	81	56	
16 mmHg	141	91	63	

Including approximately 10% to 15% dropout.
Abbreviations: mmHg = millimeters of mercury

SITES:

Approximately 90 sites in North America, South America, Israel, and Europe

SPONSOR:

KBP BioSciences Co., Ltd. [name] United States

[contact] [contact]

TABLE OF CONTENTS

518	gnatur	e Page .		2
Inv	estiga	ıtor Agı	reement	3
Su	mmar	y of Ch	anges – Amendment 2	4
Sy	nopsis			17
Ta	ble of	Conten	ıts	24
Lis	st of T	ables		28
Lis	st of F	igures		29
Lis	st of A	bbrevia	ations and Definition of Terms	30
1	Intro	duction	and Background Information	32
2	Study	y Objec	tives	35
	2.1	Primar	ry Objective	35
	2.2	Secon	dary Objectives	35
3	Study Description.			36
	3.1	Summ	nary of Study Design	36
	3.2	Risk N	Management	38
		3.2.1	Independent Data Monitoring Committee.	38
	3.3	Study	Indication	38
4	Selection and Withdrawal of Patients			39
	4.1	Inclus	ion Criteria	39
	4.2	Exclus	sion Criteria	40
	4.3	Withd	rawal Criteria	42
5	Study	y Treatr	ments	44
	5.1	Treatn	nent Groups	44
	5.2	Ration	nale for Dosing	44
	5.3	Rando	mization and Blinding	44
	5.4	Breaki	ing the Blind	45
	5.5	Drug S	Supplies	45
		5.5.1	Formulation and Packaging	45
		5.5.2	Study Drug Preparation and Dispensing	46
		5.5.3	Study Drug Administration	46

		5.5.4	Treatment Compliance	46
		5.5.5	Storage and Accountability	46
	5.6	Prior	and/or Concomitant Medications and/or Procedures	47
		5.6.1	Excluded Medications and/or Procedures	47
		5.6.2	Restricted Medications and/or Procedures	47
		5.6.3	Documentation of Prior and Concomitant Medication Use	47
		5.6.4	Management of Other Co-Morbidities	48
6	Stud	y Proce	edures	49

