INVESTIGATIONAL PRODUCT: KBP-5074

PHASE: 2

INDICATION: Uncontrolled hypertension (Grade 1 to 2 systolic hypertension – European Society of Cardiology [ESC]/European Society of Hypertension [ESH]) in patients with moderate-to-severe chronic kidney disease (CKD)

OBJECTIVES:

The primary objective of this study is to evaluate the efficacy of KBP-5074 in patients with moderate-to-severe CKD on uncontrolled hypertension (eg, Grade 1 to 2 systolic hypertension – ESC/ESH) as determined by change in trough-cuff seated systolic blood pressure (SBP) from baseline to Day 84.

The secondary objectives of this study are the following:

- To evaluate the change in trough-cuff seated diastolic blood pressure (DBP) from baseline to Day 84;
- To evaluate the change in 24-hour mean, daytime mean, nighttime mean, morning mean, last 6 hours of the dosing interval mean, SBP, DBP, mean arterial pressure (MAP), and heart rate (HR) from baseline to Day 84 in a subset of up to 40 patients per treatment group as measured by 24-hour ambulatory blood pressure monitoring (ABPM);
- To evaluate the change and percent change in urine albumin-to-creatinine ratio (UACR) from baseline to Day 84 (for patients with albuminuria [defined as UACR > 300 mg/g] or microalbuminuria [defined as UACR in the range of 30 mg/g to 300 mg/g]);
- To evaluate the change in serum aldosterone and plasma renin levels from baseline to Day 84;
- To evaluate the incidence of hyperkalemia (defined as serum potassium ≥ 5.6 mmol/L), incidence of severe hyperkalemia (defined as serum potassium ≥ 6.0 mmol/L), and incidence of patients with serum potassium > 5.0 mmol/L;
- To evaluate the change in serum potassium levels from baseline to Day 84;
- To evaluate the changes in estimated glomerular filtration rate (eGFR) and creatinine levels > 30% throughout the study period; and
- To evaluate population pharmacokinetics (PPK) of KBP-5074.

POPULATION:

The population for this study will be male and female patients 18 to 85 years of age, inclusive, with Stage 3B/4 CKD (defined as eGFR \geq 15 and \leq 44 mL/min/1.73 m², based on the isotope dilution mass spectrometry traceable Modification of Diet in Renal Disease equation version 4, according to central laboratory results at Screening). Patients are to have uncontrolled hypertension (Grade 1 to 2 systolic hypertension – ESC/ESH) defined as:

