7.2 Secondary Efficacy Assessments

Twenty-four-hour ABPM monitoring will be assessed at the visits indicated on the Schedule of Procedures (Appendix A) in a subset of up to 40 patients per treatment group. At the end of the run-in period (Visit 3), ABPM will only be assessed for those patients who agree to participate in 24-hour ABPM and still meet all of the eligibility criteria. Blood pressure and HR measurements will be obtained every 20 minutes during the interval of 06:00:00 hours to 21:59:59 hours (to coincide with the daytime, awake period) and every 30 minutes during the interval of 22:00:00 hours to 05:59:59 hours (to coincide with the nighttime, sleeping period).

During the 24-hour ABPM recording period, a diary will be provided to the patient. Instructions and training will be provided to the site staff, who will in turn provide instructions to the patient.

The key secondary efficacy variables include the following:

• Change in trough-cuff seated DBP from baseline to Day 84;

Note: Blood pressure must be measured in triplicate prior to study drug administration at the visits indicated on the Schedule of Procedures (Appendix A). Trough-cuff DBP values will be assessed based on the pre-defined blood pressure measure guideline throughout the study.

- Change in 24-hour mean, daytime mean, nighttime mean, morning mean, last 6 hours of the dosing interval mean, SBP, DBP, MAP, and HR from baseline to Day 84 as measured by 24-hour ABPM in a subset of up to 40 patients per treatment group; and
- Change and percent change in UACR from baseline to Day 84 (for patients with albuminuria [defined as UACR >300 mg/g] or microalbuminuria [defined as UACR in the range of 30 mg/g to 300 mg/g]).

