7.4 Pharmacodynamic Assessment

The pharmacodynamic (PD) variable of this study is the change in levels of serum aldosterone and plasma renin from baseline to Day 84. Serum samples for aldosterone and plasma samples for renin will be collected at the visits indicated on the Schedule of Procedures (Appendix A).

Serum/plasma samples will be stored at the central laboratory for determination of various additional biomarkers, including but not limited to galectin-3, NT-proBNP, IL-6, collagen

biomarkers, and CRP. The panel of biomarkers and time points for analysis will be determined prior to the database lock.

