9.2.3 Analysis of Safety

The assessment of safety will be based primarily on the frequency of patients with adverse events and clinical laboratory abnormalities. Other safety data will be summarized as appropriate.

All safety analyses will be conducted on the total patient cohort based on the Safety Population.

Adverse events will be coded using the Medical Dictionary for Regulatory Activities. Reports will be provided to the Medical Monitor for approval of the coded terms after the database is clean, prior to unblinding. The number and frequency of patients with TEAEs (ie, those adverse events that newly occur or worsen in severity during the study) will be summarized by system organ class and preferred term. Serious adverse events and TEAEs related to study drug will be summarized in the same manner. A list of patients with SAEs and those who discontinue from the study due to an adverse event will be provided.

Summary statistics by treatment group at baseline, at all post-randomization visits, and changes from baseline to the post-randomization visits for laboratory values will be provided. Occurrence of significant abnormalities in laboratory values from baseline will be summarized by treatment group. Vital signs, body weight, and physical examination findings will be summarized.

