9.2.4 Analysis of Pharmacokinetics

The analysis of the PK/PD relationship will be explored. Population PK models will be built using a nonlinear mixed effects modeling technique with NONMEM software based on the PPK Population. Different PK models will be attempted to fit the PK concentration-time data. After the PPK modeling, a population PD approach will be used to explore the concentration-effect relationships. Different PD models will be attempted to fit the concentration-effect data. All PD exploration will be based on the ITT Population.

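### The secondary objective on serum aldosterone and plasma renin has no clearly assigned dose-versus-placebo comparison, and the one model that might apply does not adjust for the hormone's own baseline

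*Combined protocol and SAP*

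**What the plan says.** The Synopsis (Objectives) and Section 2.2 list as a secondary objective: "To evaluate the change in serum aldosterone and plasma renin levels from baseline to Day 84". Section 7.4 places the same quantity under its own heading: "The pharmacodynamic (PD) variable of this study is the change in levels of serum aldosterone and plasma renin from baseline to Day 84". The Synopsis does likewise under Pharmacodynamic Variables: "The pharmacodynamic (PD) variable of this study is change in serum aldosterone and plasma renin levels from baseline to Day 84". Other stored biomarkers are left to be chosen later, so these two hormones are the only pharmacodynamic variable named.

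Section 7.2 introduces the efficacy list with "The key secondary efficacy variables include the following" and then gives DBP, the ambulatory pressure measures and UACR. UACR has two scales: "Change and percent change in UACR from baseline to Day 84". Aldosterone and renin have change only.

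Three analysis statements could bear on the hormones:

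- Section 9.2.2.2 and the Synopsis: "For continuous secondary efficacy variables, the same ANCOVA model will be used as the primary efficacy analysis". The dose-versus-placebo sentence follows in the same paragraph. The primary model (Section 9.2.2.1) has treatment, eGFR level and background medication as factors and baseline SBP as the covariate.
- Section 9.2.4: "After the PPK modeling, a population PD approach will be used to explore the concentration-effect relationships". This work is described as exploration in the ITT Population.
- Section 9.2.3: "Summary statistics by treatment group at baseline, at all post-randomization visits, and changes from baseline to the post-randomization visits for laboratory values will be provided". Appendix B lists aldosterone and renin among the laboratory analytes.

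**The concern.** A stated secondary objective should lead to a stated estimate. Here the objective, the variable and the analysis use different labels: secondary objective, pharmacodynamic variable, secondary efficacy variable. The reader cannot tell which analysis answers the question.

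Without a clear assignment, the model, scale and covariate for these markers may be settled after the data are seen. If the default model is applied as worded, the estimate is less precise than the same samples allow. At stake is the pharmacodynamic evidence for each of the two doses in a Phase 2 trial. SBP, DBP, ambulatory pressure, UACR and the safety monitoring do not depend on it.

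**Working it through.** **1. Which analysis serves the objective?**

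| Candidate | Covers the hormones? | Gives dose versus placebo with a CI? |
|---|---|---|
| ANCOVA (9.2.2.2) | Unclear: written for efficacy variables, hormones classed as pharmacodynamic | Yes, if it applies |
| Concentration-effect model (9.2.4) | Yes, as pharmacodynamics | No: it relates effect to concentration and is exploratory |
| Laboratory summaries (9.2.3) | Arguably, through Appendix B | No: summaries by arm, with no stated difference or interval |

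The second route is also thin at the time point of interest. Appendix A samples the hormones on Day 1, Day 84 and at Early Termination. PK samples are taken on Days 1, 14, 28 and 112 or Early Termination. A completer has no measured concentration on Day 84, so exposure then must be predicted from the model.

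**2. The plan's own figure, used for the sample size below.** Section 9.2.7 takes a 5 mmHg difference and SD 15 and asks that the 95% CI exclude 0:

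n = 2 × 1.96² × 15² / 5² = 69.1, so 70 evaluable per group; 70 × 1.15 = 80.5.

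This matches the 81 in Table 2 and the 80 in the text. It concerns SBP only. The documents give no SD, correlation or expected effect for either hormone, so everything below rests on assumed values, with 70 analysed per arm.

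**3. Cost of omitting the hormone's own baseline.** Let each visit have variance σ² and let the baseline to Day 84 correlation be rho. Assume baseline SBP explains none of the hormone change.

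- Variance of change: 2σ²(1 − rho)
- Residual variance after adjusting for own baseline: σ²(1 − rho²)
- Ratio: 2/(1 + rho)

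This gives 1.43 at rho 0.4, 1.25 at 0.6 and 1.11 at 0.8. At 1.25, 70 patients per arm carry the precision of 70/1.25 = 56.

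**4. Added cost of the untransformed scale, if the hormones are log-normal.** Simulated power for one dose against placebo, two-sided 5%, true 1.5-fold rise, rho 0.6, 70 per arm. Repeat runs agree within a point or two.

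| Log-scale SD | Change, SBP covariate | Change, with raw own baseline | Log ratio, own log baseline |
|---|---|---|---|
| 0.4 | about 100% | about 100% | about 100% |
| 0.6 | 98% | 99% | over 99% |
| 0.8 | 82% | 86% | 96% |
| 1.0 | 53% | 59% | 84% |
| 1.2 | 32% | 38% | 71% |

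At log-SD 1.0 the gap is 84 − 53 = 31 points. Own baseline on the raw scale recovers 59 − 53 = 6 of them. The other 25 come with the move to the log scale, so they depend on the skewness assumption. For a 1.3-fold rise at log-SD 1.0 the three figures are 26%, 30% and 49%. Fitting all three arms together with both doses active lowers the two untransformed columns by about 4 to 7 points at log-SD 0.8 to 1.2. In that three-arm fit at log-SD 1.0 (1.5-fold), change with the SBP covariate against the log analysis is 36% against 73% at rho 0.4, and 72% against 98% at rho 0.8.

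**The case against.** The strongest reply is that nothing expressly excludes the hormones. The list in Section 7.2 is open and limited to key variables. The objective sits directly after DBP, ambulatory pressure and UACR, and Section 9.2.2.2 speaks of continuous secondary efficacy variables in general. A reader might infer from the separate pharmacodynamic heading that the plan gives the objective no comparison with placebo at all. The documents do not support that: the exclusion would rest on silence, and summaries by arm are arguably planned. What they support is that the assignment is unclear.

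Second, serum potassium change is also a secondary objective placed outside the efficacy list, so leaving such variables to summaries is consistent practice within this protocol. That explains the omission, but it does not supply an estimate for this objective.

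Third, the baseline SBP wording applies equally to DBP, ambulatory pressure and UACR, and each variable's own baseline may have been intended. That is fair: the covariate problem is general to Section 9.2.2.2. It still applies here if the hormones fall under that model.

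Fourth, the documents say only change. They do not say raw change, and they give no distribution. A reader might infer that a real rise would easily be missed. That does not follow: at log-SD 0.4 every method has about 100% power, and at 0.6 the least efficient has 98%. The objection stands against any claim of certain loss, but not against naming the scale.

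**Conclusion.** The point holds as a gap in assignment with a conditional loss of efficiency. No section clearly commits to a dose-versus-placebo estimate for a named secondary objective. This part rests on the text alone.

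If the efficacy ANCOVA applies as worded, the variance is 2/(1+rho) times what adjustment for own baseline would give, or 1.11 to 1.43 for rho from 0.8 down to 0.4. This assumes equal variances and no help from baseline SBP. If the hormones are also right-skewed, power for a 1.5-fold rise falls by anything from nothing (log-SD 0.4) to about 31 points (log-SD 1.0) at rho 0.6. The documents cannot place the trial within that range.

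It should be corrected before unblinding. It does not bear on the primary or key secondary conclusions.

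**What to change.** In Section 9.2.2.2 and the Synopsis, state that Day 84 log aldosterone and log renin are each analysed by ANCOVA with treatment and the other factors of the primary model (eGFR level and background antihypertensive medication). Replace baseline SBP with the log of the analyte's own Day 1 value. Baseline SBP may be kept as well, since SBP is a stratification variable in Section 5.3. Report the geometric mean ratio of each dose to placebo with a 95% CI in the ITT Population.

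State how missing Day 84 values are handled and whether Early Termination samples count. The last-observation rule in Section 9.2.2.1 is written for SBP, and Section 6.6 places the Early Termination sample after study drug has stopped. Keep the concentration-effect model as exploratory.

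The cost is a few lines of text and two model fits on samples already scheduled. The small downside is that results are ratios and not absolute changes; the planned summaries by arm can still show the latter.
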